### 16.1.2 PFS Sensitivity Analyses

To assess the robustness of the primary analysis, the following analyses can be conducted:

- Per-protocol analysis: the same analysis as described above Section 16.1.1 will be repeated on PP analysis set only if PP analysis set includes less than 90% of the ITT analysis set.
- The same analysis as described above Section 16.1.1 will be repeated using results of the *clinical* review from IRC, corresponding listing will also be produced.
- The same analysis as described above Section 16.1.1 will be repeated considering all death as event.
- The same analysis as described above Section 16.1.1 will be repeated considering all death and start of new anti-cancer treatment as event.
- To address the bias due to different times of assessment of disease progression caused by different treatment schedules, the same analysis as described above Section 16.1.1 will be repeated considering date of planned imaging visits instead of date of actual imaging visits. If an event is observed between two planned visits, it will be assigned to the previous one. The planned day for EOEA visit will be assigned as the planned day for the last available efficacy assessment visit.
- The same analysis as described above Section 16.1.1 will be repeated excluding subjects who met the inclusion criteria 3 as defined in protocol version 1.0 (17 November 2014) but who do not meet the updated inclusion criteria 3 as defined in protocol version 2.0 (20 April 2016). Please refer to [Appendix 2](#) for the details for inclusion criteria 3.
- The same analysis as described above Section 16.1.1 will be repeated based on the stratification factors based on eCRF data instead of IWRS data.

Results of PFS primary and sensitivity analyses (hazard ratio and 95%CI) will be displayed using a forest plot.

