Tumor assessment: Tumor assessment will be performed according to RECIST version 1.1. The baseline tumor assessment is to be performed during the screening period within 28 days before the start of trial treatment. Computed tomography (CT) or magnetic resonance imaging (MRI) with contrast enhancement is recommended for tumor assessment. Subsequent tumor response evaluations will be assessed every 6 weeks (± 3 days) starting from the randomization day until occurrence of PD regardless of any cycle delay. If treatment is discontinued for reasons other than PD, subjects will continue to have tumor assessments until either PD, the start of a new antitumor treatment, death, the termination of the trial, or loss of follow up, whichever comes first. If symptoms are suggestive of PD, subjects will be evaluated by imaging studies thereafter for documentation and confirmation of the tumor responses. The details of documentation of tumor assessment is described in Section 7.3.1.

Safety follow-up period: All subjects in Arm A and B will be followed up continuously for safety evaluations according to schedule of assessments in Table 1.1 starting from date of first signature of informed consent. A Safety Follow-up visit will be performed 30 days (± 3 days) after the last dose of trial treatment or immediately before starting any new antitumor treatment. During the treatment period, additional safety evaluations will be on a weekly basis (Arm A only) for physical examination, vital signs, documentation of AEs and concomitant medications, and also at the start of each cycle (for both arms) for ECOG performance status, ECG, hematology, biochemistry and urinalysis. Survival data and any information on new antitumor treatments will be collected every 3 months after the EOEA visit until either death, loss of follow up, or the termination of the trial, whichever comes first.

Primary and secondary endpoints: The primary endpoint of this trial is PFS time, as assessed by an IRC. Secondary endpoints include PFS time, as assessed by the Investigator, OS time, BOR rate, DCR, duration of response, and safety (see Section 8).

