The treatment effect expressed as hazard ratio of cetuximab plus CTX to CTX alone including 95% CI on PFS time will be primarily evaluated using a stratified Cox proportional hazard model, including treatment and the randomization strata (as specified in the IWRS, see Section 7.2): ECOG performance status (0 versus 1) and primary tumor site (oral cavity versus hypopharynx versus others). Each strata will define separate baseline hazard functions (using the 'STRATA' - statement in SAS Proc PHREG), i.e. for the  $i$ -th stratum the hazard function is expressed as:  $h(i;t) = h(i,0;t) \exp(x\beta)$ , where  $h(i,0;t)$  defines the baseline hazard function for the  $i$ -th stratum and  $x$  defines the treatment arm (0=CTX only, 1=CTX + cetuximab) and  $\beta$  the unknown regression parameter.

Ties will be handled by replacing the proportional hazards model by the discrete logistic model (Ties=Discrete option in SAS Proc PHREG). This is a bridging trial; in discussion with Chinese Health Authority, this trial would be regarded as positive if the point estimation of the stratified hazard ratio is less than or equal to 0.77 (retaining at least 50% of the estimated treatment effect of EXTREME trial).

The PFS time of the 2 treatment arms will be described by means of Kaplan-Meier survival curves (product-limit estimates) and associated summary statistics (median PFS time, corresponding two-sided 95% confidence intervals, minimum, maximum, Q1, Q3). Survival estimates at certain time points (3-, 6-, 12-, 18-, 24 months and every 6 months thereafter as applicable), and number of subjects under risk will also be provided. The confidence intervals for the median will be calculated according to Brookmeyer and Crowley (1982) and confidence intervals for the survival function estimates will be derived using the log-log transformation according to Kalbfleisch and Prentice (1980) (conftype=loglog default option in SAS Proc LIFETEST).

The number of events (PD/death) will also be presented within the same table.

An additional table will provide frequencies for events and censoring status by treatment arm according to the following categories:

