- Events: Radiological PD based on existing lesions (progressive disease reported for target and/or non-target lesions) / Radiological PD based on new lesions (new lesion(s) is/are reported) / Radiological PD based on existing and new lesions (both progressive disease reported for target and/or non-target lesions and new lesion(s) are reported) / Death within 60 days
- Censoring: Death not within 60 days / Censored at randomization / Lost to follow-up or withdraw consent / Due to data cut-off

Subjects will be considered as “censored at randomization” in case they have no tumor assessment at baseline and no tumor assessment after start of treatment and no radiological PD or death.

They will be considered as censored due to “Lost to follow-up/withdraw consent” in case they have no PD or death before they are lost to follow-up/withdraw consent.

They will be considered as censored “due to cut-off” in case they have no PD or death before the trial data cut-off.

A listing will display information on event and censoring including the following:

- Subject identification number,
- Treatment arm
- Randomization Date
- Last tumor assessment date before cut-off date
- Death date
- Progression date (IRC)
- PFS (IRC): Censoring Flag (Yes/No)/ Description of the Event/Censoring/ PFS (months)

A scatter plot will be produced to compare planned (y-axis) and actual (x-axis) relative day of tumor assessments by treatment arm (2 colors will be used to clearly identify treatment groups). The planned day for EOEA visit will be assigned as the planned day for the last available efficacy assessment visit.

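### The planned-visit PFS sensitivity analysis dates PD found on an unscheduled scan 6 weeks earlier than the same PD found on schedule, so its hazard ratio shifts if such scans differ by arm

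*SAP*

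**What the plan says.** SAP 16.1.2 lists analyses that may be run to test the primary PFS result. One has the stated aim "To address the bias due to different times of assessment of disease progression caused by different treatment schedules". It repeats the 16.1.1 analysis with planned imaging dates in place of actual ones, and then gives two further rules. The first covers events that fall off the visit grid: "If an event is observed between two planned visits, it will be assigned to the previous one". The second is specific to scans recorded at the end of efficacy assessment (EOEA): "The planned day for EOEA visit will be assigned as the planned day for the last available efficacy assessment visit".

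The output goes beside the primary result: "Results of PFS primary and sensitivity analyses (hazard ratio and 95%CI) will be displayed using a forest plot".

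Three other places bear on this.

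- **Unscheduled imaging.** Tumor assessments are 6-weekly (± 3 days), but Protocol 5.1 also foresees scans prompted by symptoms: "If symptoms are suggestive of PD, subjects will be evaluated by imaging studies thereafter for documentation and confirmation of the tumor responses". Protocol 7.3.2 says the same.
- **Ties.** Because the analysis repeats 16.1.1, it takes over that section's ties rule: "Ties will be handled by replacing the proportional hazards model by the discrete logistic model".
- **What counts as an event.** The list of PFS event categories in SAP 16.1.1 ends "new lesion(s) are reported) / Death within 60 days", so the word event in the dating rule can be read to include deaths.

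**The concern.** Within this analysis, PD found at a scheduled scan takes the planned date of the visit that found it. PD that arises in the same interval but is found on an unscheduled scan takes the date of the visit before. The date therefore depends on how the PD was found, which is the kind of timing difference the analysis is meant to remove.

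The hazard ratio is affected when the share of unscheduled detections differs by arm. The documents give no rate and no arm difference. Arm A is seen weekly for cetuximab (Protocol 7.1.2), Arm B is not, and the trial is open-label, so a difference is possible in either direction. More unscheduled PD in Arm A pushes the HR up; more in Arm B pushes it down, in favour of cetuximab.

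This is the only planned analysis aimed at assessment timing. A reader who wants to know whether timing drove the primary estimate will look at this row of the forest plot.

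Two side issues make the row harder to read. Planned dates are heavily tied by design, so the discrete logistic model estimates a per-interval odds ratio, which is not comparable with the primary HR. And the EOEA sentence can move a PD scan recorded at that visit to an earlier planned day.

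**Working it through.** **Yardstick.** The plan states no figure for this analysis. Its threshold reproduces from the 46% risk reduction in Protocol 3.7.2: 1 − 0.5 × (1 − 0.54) = 0.77. With 144 events and 2:1 allocation, the SE of the log HR is 1/√(144 × 2/9) = 0.177.

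**Date arithmetic (no assumptions).** Take planned visits at days 42, 84 and 126.

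| Scan showing PD | SAP rule | Same PD found on schedule |
|---|---|---|
| Scheduled, done late on day 90 | 84 | 84 |
| Unscheduled, day 65 | 42 | 84 |
| Unscheduled, day 30 | 0 (randomization) | 42 |

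The gap for each unscheduled PD is 42 days, or 42/30.4375 = 1.38 months.

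**Effect on the HR (simulation).**

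- From the documents: 240 subjects, 2:1, six strata (2 × 3), analysis at the 144th event, 6-weekly scans within ± 3 days, control median 3.3 months (Protocol 3.7.2), and median post-progression survival of 5 months (the PFS–OS gap in Protocol 5.2).
- Assumed: true HR 0.77, the unscheduled shares of PD, modest prognostic differences between strata, 18-month accrual, 3% drop-out per month, and a pre-progression death hazard of 10% of the PFS hazard (about 17% of events are deaths). Unscheduled PD falls at least 4 days from any planned visit.
- Runs: 1,500 trials per unequal-share scenario and 1,000 for 25/25 and 0/0. All fits are stratified.

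Each cell shows actual dates / SAP rule / on-schedule dating.

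| Unscheduled % (A/B) | Ties=Discrete (SAP) | Efron |
|---|---|---|
| 35/15 | 0.802 / 0.807 / 0.758 | 0.803 / 0.819 / 0.777 |
| 15/35 | 0.740 / 0.707 / 0.750 | 0.743 / 0.729 / 0.769 |
| 10/5 | 0.778 / 0.768 / 0.755 | 0.780 / 0.785 / 0.774 |
| 5/10 | 0.761 / 0.741 / 0.753 | 0.764 / 0.761 / 0.771 |
| 25/25 | 0.762 / 0.749 / 0.745 | 0.764 / 0.767 / 0.764 |

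Under the SAP's ties method, the SAP rule differs from on-schedule dating by ln(0.807/0.758) = 0.063 at 35/15, ln(0.707/0.750) = −0.059 at 15/35 and ln(0.768/0.755) = 0.017 at 10/5. About 9 to 11 of the 144 events are dated to randomization at 35/15 or 15/35, and 3 at 10/5.

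**Is the SAP rule worse than leaving actual dates alone?** Share of trials in which it lands farther from on-schedule dating than actual dates do:

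| | 35/15 | 15/35 | 10/5 | 5/10 |
|---|---|---|---|---|
| Discrete | 55% | 76% | 31% | 38% |
| Efron | 73% | 71% | 43% | 40% |

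**Large-sample checks.**

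- With 1.5 million subjects, unstratified, with deaths, the pattern is the same. Efron gives 0.790/0.805/0.772 at 35/15 and 0.754/0.741/0.772 at 15/35; Discrete gives 0.790/0.792/0.754 and 0.751/0.720/0.754.
- A separate grouped-time model (400,000 subjects, no deaths) compares the SAP rule with next-visit dating. It gives 0.81 against 0.77 at 30/10, 0.73 against 0.77 at 10/30, and 0.77 for both at 20/20. With true HR 1, 30/10 gives 1.06 against 1.00.
- With scheduled scans 0–14 days late in one arm only, the SAP rule returns the on-schedule value (Efron 0.772–0.773, Discrete 0.745).

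**Ties and deaths alone.** With no unscheduled scans, Ties=Discrete gives 0.753 on planned dates against 0.767 on actual dates, while Efron gives 0.772 against 0.770. Moving deaths back as well gives 0.747 instead of 0.753.

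**The case against.** **The rule was written for scan drift.** The bullet speaks of different treatment schedules and never mentions unscheduled scans. A late scan does fall between two planned visits, and assigning it to the previous one is right. This stands for late scans, and the simulation confirms it. But the sentence is not limited to them, and nothing else in the SAP removes symptom-driven scans from it.

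**The shares are invented.** This also stands. 35/15 and 15/35 are deliberately wide. At 10/5 and 5/10, under the SAP's own ties method, the rule is no worse than actual dates in most trials, and at 10/5 it moves the mean HR toward the on-schedule value. With Ties=Discrete, 35/15 moves the HR only 0.005 from actual dates. Only 15/35 is clearly adverse.

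**The benchmark favours the remedy.** Next-visit dating is close to on-schedule dating almost by construction, so its being nearer in 88–92% of trials is weak evidence. The better argument is internal consistency: every other PD in this analysis is dated to the visit that found it.

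**The side issues are small.** A death has no imaging visit, and the censoring table in SAP 16.1.1 dates it to the day of death, so moving deaths may not be intended. The EOEA sentence need not move anything if the last efficacy visit is the EOEA visit itself. Both are ambiguities, not certain errors.

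**No decision depends on it.** The analysis is exploratory and optional, the 0.77 criterion uses actual dates, and SAP 16.1.1 already promises a display of timing by arm: "A scatter plot will be produced to compare planned (y-axis) and actual (x-axis) relative day of tumor assessments by treatment arm". This limits the weight of the point but does not make the rule right.

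**Conclusion.** The concern holds, at low weight. The 42-day difference follows from the text alone. The effect on the HR rests on assumed unscheduled shares. It is close to nil when the shares are equal, about 0.02 in log HR when they differ by 5 points, and about 0.06 when they differ by 20 points. The last is roughly a third of the SE of 0.177.

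Compared with simply using actual dates, the rule moves the HR the wrong way in both directions for large share differences with Efron ties. With the SAP's Ties=Discrete this is clear only when Arm B has many more unscheduled PDs. Separately, Ties=Discrete on planned dates lowers the HR from 0.767 to 0.753 even with no unscheduled scans, a small shift toward cetuximab that comes from the model and not from assessment timing.

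The primary analysis and its criterion are not affected. The point is worth correcting because the rule works against the analysis's own stated purpose and the result is shown beside the primary HR.

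**What to change.** In SAP 16.1.2, replace the between-visits sentence and the EOEA sentence with rules to this effect:

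- Each scheduled scan, early or late, takes the date of its own nominal planned visit.
- PD first documented on an unscheduled scan takes the next planned visit date, but no later than the date of death. PD documented before the data cut-off stays an event.
- Deaths keep their actual date.
- Censoring uses the nominal planned date of the last evaluable scan.
- EOEA scans are classed as scheduled or unscheduled and follow the same rules.
- Efron ties are used in this analysis, because planned dates are heavily tied.

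The planned visits also need one starting point: Protocol 5.1 and SAP section 6 count from randomization, Protocol 7.1.4 and 7.3.2 from first dose.

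In the simulation this wording gives, against on-schedule Efron values, 0.784 vs 0.777 (35/15), 0.762 vs 0.769 (15/35), 0.776 vs 0.774 (10/5), 0.769 vs 0.771 (5/10) and 0.765 vs 0.764 (25/25).

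The cost is two sentences, one ties option and a scheduled/unscheduled flag per scan. The SAP does not list this flag, though the planned-versus-actual scatter plot already needs a planned day for each assessment. PFS times in this analysis become slightly longer, and its ties option differs from the primary's, which the forest plot should note. Keeping PD found before cut-off as an event when its next planned visit falls later leaves a residual of up to about 0.01 in log HR. Censoring those subjects at the preceding visit would remove it but discard documented PD.

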### 16.1.3 PFS Subgroup Analyses

Subgroup analyses will comprise univariable unstratified analyses considering the subgroups as defined in Section 10. To assess the heterogeneity of treatment effects across the subgroups levels Cox proportional hazards model will be performed for PFS time as dependent variable and with subgroup type, the treatment arm assignment and with and without the treatment by subgroup type interaction as explanatory variables. P-values for the interaction test will be provided together with the hazard ratios (CTX+Cetuximab over CTX) and 95% CIs.

A forest plot of hazard ratio by subgroups will be provided for illustration. It will include, for each subgroup, the number of subjects per subgroups and treatment group, the number of events with related median (in month) by treatment group and hazard ratio (CTX+Cetuximab over CTX) with the corresponding 95% CIs.

### 16.1.4 PFS Exploratory Analysis

To explore the treatment effect when adjusted for exploratory variables of potential prognostic values, a **multivariable Cox regression** analysis will be performed. (The potential baseline prognostic factors variables used for this analysis will be the subgroup variables as defined in Section 10.2)

A stepwise selection procedure will serve to identify explanatory variables of potential prognostic values additional to the randomization strata (as documented in the eCRF) which will be included in all models during the selection procedure. The Cox proportional hazard model is defined as:  $h(t) = h(0;t) \exp(X\beta)$ , where  $h(0;t)$  defines the baseline hazard function and  $X$  defines the vectors of explanatory variables and  $\beta$  the unknown vector of regression parameters. Variables are entered into and removed from the model in such a way that each forward selection step can be followed by one or more backward elimination steps. The stepwise selection process terminates if no further variable can be added to the model or if the variable just entered into the model is the only variable removed in the subsequent backward elimination. The level of significance for an explanatory variable to enter the model is set to 0.15 and the significance level for removing is set to 0.40. This analysis will be performed using the stepwise selection method available in SAS (Proc PHREG). Once this procedure stops, the factor 'treatment group' will be added to the final model in order to evaluate the effect of treatment on PFS when adjusted for the selected explanatory variables. The hazard ratios of all selected explanatory variables and of the treatment effect will be reported including two-sided 95% confidence intervals. If there is a treatment by covariate interaction present for any of the covariates including in the model (as tested in subgroup analyses, see section 16.1.3), the corresponding parameter will not be considered for the stepwise analysis.

To include baseline variables into Cox's proportional hazards model, in case of low numbers of subjects within a category (< 10 subjects), categories will be pooled as described in the section 10.

## 16.2 Secondary Endpoint Analyses

The secondary endpoints include PFS time, as assessed by the Investigator, OS time, BOR, DCR, and duration of response (DOR). The following analyses will be performed on the ITT analysis set.

The following secondary endpoints will be analyzed using both IRC radiological assessments and investigator assessments:

- BOR
- DCR
- DOR

### 16.2.1 PFS Time by Investigator Assessment

PFS time, as assessed by the Investigator, is defined as the duration (in months) from randomization until first observation of radiologically confirmed PD (by the Investigator), or death due to any cause when death occurs within 60 days after the last tumor assessment or randomization (whichever is later). The same censoring rule as with the PFS time assessed by IRC is applied.

The date of first PD radiologically confirmed will be based on the earliest imaging date for the tumor assessment visit where overall assessment visit is PD.

In case there are several dates of scans within the same tumor assessment visit, the earliest date will be used as the date of first confirmed PD.

The same analyses as described Section 16.1.1 will be conducted, the corresponding listing will be produced.

Subgroup analyses will be performed for predefined baseline factors (see Section 15.1.3).

The PFS time, as assessed by the investigator, will be described by means of Kaplan-Meier survival curves (product-limit estimates) for each treatment arm.

The concordance between the IRC radiology assessment and the investigator assessment will be tabulated by treatment group including the following information:

- PFS event by source (Investigator only / IRC only / IRC and Investigator / no PFS event)
- Difference in days (PFS date assessed by IRC – PFS date assessed by investigator)
  - $\leq -30$  days
  - $>-30$  days to  $< 30$  days
  - $\geq 30$  days
- Overall concordance of PFS

- Agreement
- Disagreement
- Both no PFS event
- Summary of difference (days)

## 16.2.2 Overall Survival Time

OS time is defined as the time (in months) from randomization to the date of death. If a subject is alive at the time of analysis, survival time will be censored at the last date when the subject is known to be alive. If this date is after data cut-off, subjects will be censored at the date of data cut-off.

The latest of the following dates will be used to determine the last date known to be alive:

- All patient assessment dates (blood draws (laboratory, PK), vital signs, performance status, ECG, tumor assessments)
- Start and end dates of anti-cancer therapies administered after trial treatment discontinuation.
- AE start and end dates
- Last date of contact collected on the 'Survival information' eCRF (do not use date of survival follow-up assessment unless status is 'alive')
- Study drug start and end dates
- Randomization date

The same analyses as described Section 16.1.1 will be conducted.

Subgroup analyses will be performed for predefined baseline factors (see Section 15.1.3 and use OS instead of PFS).

The OS time will be described by means of Kaplan-Meier survival curves (product-limit estimates) for each treatment group and a forest plot will also be provided as described for PFS

An additional table will provide frequencies for events and censoring status by treatment group according to the following categories:

- Events: Death
- Censoring: At data cut-off (administrative censoring) / Before data cut-off (non-administrative censoring)

Subjects last known to be alive before data cut-off, subjects who withdrew consent or subjects lost to FU before end of trial will be considered as censored before data cut-off.

A listing will display information on event and censoring including the following:

- Subject Id

- Treatment Arm
- Randomization Date
- Death date
- Last date known to be alive
- Date of first cetuximab administration given as Anti-cancer Drug Therapy after Discontinuation of the trial treatment
- OS: Censoring Flag (Yes/No)/ OS (months)

